## 5.1 Inclusion Criteria

-Patient plans to have partial liver resection for primary liver pathology or metastatic disease

-Patients is able to comprehend and willing to sign the written consent form

## 5.2 Exclusion Criteria

-Patients with age less than 18 years

-Patients identified as part of the vulnerable populations as defined in the current application, except women with child bearing potential with negative pregnancy test

# 6. STUDY VISITS

Patients planned to undergo partial hepatectomy for primary or metastatic hepatic pathology will be screened for eligibility to participate in this study. Objectives, methods of data

collection, and analysis will be discussed. After answering all patient questions and explaining the patient rights including refusal to participate, the patient will be offered to participate in the study. Patients who will accept to participate will be asked to sign the participation consent form. It is a prospective data collection without interference with the treatment plan.

For Aim 1, CO will be monitored before a patient's liver resection, and at 4- and 24-hours post-resection.

For Aim 2, CT scans of liver volume will be performed at one and three months posthepatectomy, as well as liver function tests PH.

## 6.1 Withdrawal of Participants:

The PI can remove a participant from the research study without the participants approval. Possible reasons include failure to follow instructions, or if the PI decides that the research study is no longer in the participant's best interest.

During the study period, the patient can ask to withdraw from the study without that decision interfering with his/her treatment plan.

For this purpose, a letter addressed to the PI or the provider in charge of follow up is needed. The Physician will inform the PI who will withdraw the patient information from the database.

If the study is terminated for any other reason, the PI will be entitled to send a notification letter to all participants.

The doctor/PI will speak to the participant about the withdrawal and the participant will have a chance to ask questions if this were to happen.

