#### Analyses:

All results will be collected in Excel Document. Analyses of groups based on the extent of liver resection and CO production. Results of different subgroups will be analyzed; comparison between groups will be performed by fisher test, paired and unpaired student t test, main Whitney test or ANOVA with repeated measurements when appropriate. Significance is defined as p<0.05.

Potential problems and alternative strategy: It is possible that HO-1 induction varies according to preoperative and intraoperative factors beside the patient own ability to induce HO-1. The most important known other factors are smoking and intraoperative blood transfusion will be reported in the study, however, other factors may exist and influence the result of this study. Preoperative factors may include preoperative use of chemotherapy and the presence of underlying liver cirrhosis. Intraoperative factors may include operative time and surgical technique (open or minimally invasive). In case of significance variance between patient s in the same group (same percentage of PH) Subgroup analysis including different variants (preoperative chemotherapy, perioperative

	blood transfusion and onen vorsus minimally
	blood transfusion and open versus minimally
	invasive technique) will be used to assess the
	effect of these factors.
Study Population:	125 participants enrolled locally; 125
	enrolled worldwide
Inclusion Criteria:	1-Patients plans to have partial liver
	resection for primary liver pathology or
	metastatic disease
	2-Patients able to comprehend and willing to
	sign the written consent form
Exclusion Criteria:	1-Patients with age less than 18 years
	2-Patients identified as part of the vulnerable
	populations as defined in the current
	application, except women with child bearing
	potential with negative pregnancy test
Study Treatment:	For Aim 1, after the patient's procedure, they
	will have to exhale into the device listed for
	collecting exhaled air specimen.
	For Aim 2, the patient's blood samples that
	are routinely collected after a hepatectomy
	will be used for analyzing serum protein,
	Albumin, AST and ALT, alkaline phosphatase,
	and bilirubin level.
	The duration of an individual's participation
	will be about 3 months +/- 2 weeks.
Study Procedures and Assessments:	Aim 1:
	Procedures and Methods
	- Protocol:
	For collecting exhaled air specimen, each
	patient will be instructed to exhale
	completely, and then

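### Section 6.1 removes a withdrawing patient's information from the database, so valid data already collected are lost and event rates may be understated

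*Combined protocol and SAP*

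**What the plan says.** Section 6.1 (Withdrawal of Participants) describes two routes out of the study.

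- **Patient-initiated.** "During the study period, the patient can ask to withdraw from the study without that decision interfering with his/her treatment plan". The patient sends a letter, and then "The Physician will inform the PI who will withdraw the patient information from the database". Removal follows from the withdrawal itself, not from a request for deletion, and there is no exception for data already recorded.
- **PI-initiated.** "The PI can remove a participant from the research study without the participants approval". The reasons given are open-ended, and the text does not say what happens to that participant's data.

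The Protocol Summary gives a sample of 125 with no derivation. Its analysis text lists candidate tests and adds "Significance is defined as p<0.05". Neither the summary nor the numbered sections say that data collected before withdrawal are retained, define an analysis population, require withdrawals to be counted or reported, or give a missing-data method.

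**The concern.** The exposure and most of the short-term outcomes are on file long before participation ends. A patient who withdraws in the second or third month has already supplied what Aim 1 and Aim 2.2 need, and only the later CT volumes would truly be missing. Deleting the whole record turns a partly missing case into one that leaves no trace in the analysis.

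Two things are at stake. The first is precision, because every deletion reduces a sample of 125 that has no stated allowance for loss. The second is selection. The second hypothesis (section 2) and Aim 2.2 draw their information from patients who recover poorly. If those patients withdraw more often, the rule removes events that had already been observed.

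**Working it through.** **Step 1: what a withdrawal would delete.** The assessment times are:

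- CO in breath and arterial blood: "For Aim 1, CO will be monitored before a patient's liver resection, and at 4- and 24-hours post-resection" (section 6; also 7.1 and 7.2).
- INR and bilirubin criteria: postoperative day 5 (Protocol Summary, Aim 2 procedures).
- Graded complications: to 30 days (Protocol Summary, Aim 2.2 design).
- CT volumetry: one and three months (section 7.3).
- Participation: about 3 months, give or take 2 weeks (section 3).

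A patient withdrawing at week 6, for example, has everything on file except the three-month CT. Section 6.1 as written discards all of it.

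**Step 2: event rate.** The plan has no figure to reproduce, and it gives no event or withdrawal rate. Only N = 125 comes from the documents. Assume 12 liver-failure cases, a withdrawal share w of 15% or 25% among cases, and 3% among the other 113.

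Observed rate = 12(1 − w) / (125 − 12w − 113 × 0.03)

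- No deletion: 12/125 = 9.6%.
- w = 15%: 10.2/(125 − 1.8 − 3.39) = 10.2/119.8 = 8.5%.
- w = 25%: 9/(125 − 3 − 3.39) = 9/118.6 = 7.6%.

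About 2 to 3 of the 12 events are lost. This calculation contains no CO variable, so it speaks to prevalence only.

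**Step 3: association of CO with morbidity.** Assume the 125 are split into low-CO and high-CO halves (62.5 each) with true morbidity of 30% and 15%. The split is not in the plan. The true odds ratio is (0.30/0.70)/(0.15/0.85) = 2.43 and the risk difference is 0.15. Power is about 0.52 at two-sided 0.05 (the plan does not state sidedness). Deletion multiplies the odds in each half by (1 − withdrawal among poor recoveries)/(1 − withdrawal among good recoveries).

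- *Unrelated to outcome or CO, 10% throughout:* about 112 patients remain (125 × 0.90 = 112.5). The odds ratio and risk difference are unchanged, and power is 0.48.
- *Outcome only, 40% of poor and 5% of good recoveries:* both odds are multiplied by 0.60/0.95, which cancels, so the odds ratio stays 2.43. Observed risks are 0.18/0.845 = 0.213 and 0.09/0.8975 = 0.100. The risk difference falls to 0.11 and power to 0.37.
- *Outcome and CO jointly, 40% of poor recoveries in the low-CO half, 20% in the high-CO half, 5% of good recoveries:* odds ratio 2.43 × (0.60/0.80) = 1.82. Observed risks are 0.213 and 0.12/0.9275 = 0.129. The risk difference is 0.08 and power is 0.22.

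**Step 4: association of CO with regeneration.** In a simulation with a true correlation of 0.30, deleting 20%, 40% or 80% of the worst fifth on the outcome, and 5% of the rest, gives 0.295, 0.286 or 0.257. The attenuation is small unless selection is extreme.

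**Step 5: with data retained.** Outcomes recorded before withdrawal stay in, so the Step 2 rate remains 12/125 = 9.6% if all 12 events preceded withdrawal. CT volumes due afterwards are still missing.

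**The case against.** The strongest reply is that little will be lost in practice. Formal withdrawal needs a letter. The study-specific breath tests end at 24 hours, and the later scans and blood tests are routine care, so there is little study burden to withdraw from. A patient who merely misses a scan has not withdrawn, and section 6.1 does not delete that record. This stands as a limit on size: recovery-related withdrawal is possible, but the documents give no ground for calling it likely. It does not justify a rule that discards good data from those who do withdraw.

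The wording might also mean only stopping collection or removing identifiers. If so, the text does not say it and still needs amending. The consent pages are not available for review, so what participants are told about retention is unknown. That is why the fix is conditional on consent.

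Three stronger readings are tempting and are not supported:

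- *That the PI can delete patients who are too ill for the breath hold.* A reader might infer this from "Possible reasons include failure to follow instructions". But the removal sentence belongs to the patient's letter route, and the PI route is silent on data. The Protocol Summary describes an adjustable timer for patients who cannot hold their breath, arterial COHb needs no breath hold, and nothing makes a failed hold a ground for removal.
- *That the CO associations are biased.* Step 3 shows that withdrawal related to outcome alone leaves the odds ratio intact. It narrows the risk difference and costs power.
- *That the fall from 9.6% measures such bias.* The aims concern associations, and that figure is a prevalence under assumed rates.

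**Conclusion.** The point holds in a limited form. For patient-initiated withdrawal, section 6.1 states a rule, not a gap. Followed as written, it discards CO, day-5, 30-day and possibly one-month data that are already valid and complete, and nothing else in the documents overrides it.

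The loss of precision is certain for any withdrawal. A lower observed event rate follows only if poor recoveries withdraw more often; under the assumed rates it is 7.6–8.5% against 9.6%. Distortion of the odds ratio further requires that withdrawal depend jointly on outcome and CO. All rates used here are assumptions, and with few or unselective withdrawals the effect would be small. This is a worthwhile, inexpensive correction, not a defect that undermines the study.

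**What to change.** Amend section 6.1 and the matching consent wording as follows:

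- Withdrawal stops further data collection.
- Data collected up to that date are kept and analysed where consent allows, unless the participant asks in writing for deletion. Such requests are honoured and counted separately.
- State the same rule for participants removed by the PI, where the text is now silent.
- Report all withdrawals and removals by timing, reason, CO level and resection group.

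The cost is an IRB amendment to protocol and consent wording, with no effect on care. The fix is partial: outcomes due after withdrawal, chiefly the later CT volumes, remain missing and should be reported as such.

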## 7. STUDY ASSESSMENTS

This study is a prospective data collection and thus poses no associated health risks.

- 7.1 Measuring CO by exhaled air using a smokerlyzer device pre-liver resection, and at 4and 24-hours post resection
- 7.2 Measuring carboxyhemoglobin (COHb) in arterial blood gas pre-liver resection, and at 4 and 24 hours post resection
- 7.3 CT scan at 1 and 3 months post liver resection

#### 8. STUDY ETHICAL CONSIDERATIONS

The investigator agrees that the study will be conducted according to Good Clinical Practice principles of the ICH E6 (R1), ISO 14155 and the principles of the World Medical Association Declaration of Helsinki 1964 (including all amendments and Notes of Clarification). The Investigator will conduct all aspects of this study in accordance with all national, state, and local laws or regulations.

## 9. ADMINISTRATIVE CONSIDERATIONS

All laboratory specimens, evaluation forms, reports, and other records will be identified in a manner designed to maintain subject confidentiality. All records will be kept in a secure storage area with limited access. Clinical information will not be released without the written permission of the subject (or the subject's guardian), except as necessary for the FDA (or other international regulatory agency), or the IRB/IEC.

The Investigator and all employees and coworkers involved with this study may not disclose or use for any purpose other than performance of the study, any data, record, or other unpublished confidential information disclosed to those individuals for the purpose of the study.

